4.2.3.2. Second Supplementary Analyses

The details of the second supplementary estimand can be found in Table 4–6 and Table 4–7. Similar analyses steps (i.e. imputation, modeling and combining results) as for the first supplementary analysis will be applied to the secondary supplementary analysis (see Section 4.2.3.1).

For the intake of prohibited medication and permanent treatment discontinuation after which participants initiated alternative VMS treatments and interruption/discontinuation in intake of adjuvant endocrine therapy, the composite strategy will be used to handle the data. The attributes for this estimand are the same as the main estimand except for following:

• Variable:

o Change in frequency of moderate to severe HF from baseline to Week 4 in the absence of ICEs (i.e. intake of prohibited medication or initiation of alternative

version 3.0 Page: 39 of 87

VSM treatment after permanent discontinuation of randomized treatment or interrupted/discontinued adjuvant endocrine therapy) or no change from baseline otherwise.

- Change in frequency of moderate to severe HF from baseline to Week 12 in the absence of ICEs (i.e. intake of prohibited medication or initiation of alternative VSM treatment after permanent discontinuation of randomized treatment or interrupted/discontinued adjuvant endocrine therapy) or no change from baseline otherwise.
- Intercurrent Events (ICEs): see Table 4–6

version 3.0 Page: 40 of 87

Table 4-6: Second Supplementary Estimand: ICEs and Strategies to address them

ICEs ^a	Reason for ICE	Strategy	Data handling method
Temporary Treatment interruption ^b	AEs (treatment related/unrelated)	Treatment policy	Utilise the collected data after ICE.
	COVID-19 and administrative reasons	Hypothetical If participant complied with treatment	Model outcomes during the ICE under the hypothetical scenario.
Permanent discontinuation of randomized treatment	AEs (treatment related/unrelated) or Lack of efficacy		
	For participants who remained untreated/on background therapy.	Treatment policy	Utilise the collected data after ICE.
	For participants who initiate alternative VMS treatment	Composite Treatment failure (i.e. no change from baseline)	Model outcomes after the ICE under the treatment failure.
	Other treatment- unrelated reasons, including COVID-19	Hypothetical If participant did not discontinue the randomized treatment.	Model outcomes after the ICE under the hypothetical scenario.
Intake of prohibited concomitant medication having impact on efficacy	All reasons	Composite Treatment failure (i.e. no change from baseline)	Model outcomes under the treatment failure during the period of confounding.
Interruption/Disc ontinuation in intake of adjuvant endocrine therapy ^c	No reasons collected	Composite Treatment failure (i.e. no change from baseline)	Model outcomes under the treatment failure during the period of confounding.

ICE=Intercurrent event, AE=Adverse event, VMS = Vasomotor symptoms

- a) ICEs will be reviewed at the Blinded Review Meeting prior to the study unblinding
- b) Definition of temporary treatment interruption:
 - Week 1 = Treatment taken on <5/7 days during week 1.
 - Week 4 = Treatment taken <80% during weeks 1-4 OR treatment taken on <5/7 days during either week 3 or 4.
 - Week 8 = Treatment taken <80% during weeks 1-8 OR treatment taken on <5/7 days during either week 7 or 8.
 - Week 12= Treatment taken <80% during weeks 1-12 OR treatment taken on <5/7 days during either week 11 or 12.
- c) Definition of interruption/discontinuation in intake of adjuvant endocrine therapy:
 For participants using tamoxifen: reduction of at least 50% of planned daily dosage taken during week 1, weeks 3 and 4, weeks 7 and 8 or weeks 11 and 12 compared to baseline

version 3.0 Page: 41 of 87

For participants using aromatase inhibitor: reduction of at least 30% of planned daily dosage taken during week 1, weeks 3 and 4, weeks 7 and 8 or weeks 11 and 12 compared to baseline

Table 4–7: Second supplementary estimand data handling and missing data imputation strategy.

Pattern ID	ICE and the associated reason	ICE strategy and data handling	Reference group for modeling the distribution of missing or unobservable data
N/A	Intake of prohibited medications and Interruption/Discontinuation in intake of adjuvant endocrine therapy ° Any reason	Composite strategy Treatment failure (i.e. no change from baseline.) Discard the collected data after the intake of prohibited medication(s) for a certain time frame based in the medication class (See Section 6.4.3 for details) and assign the value of zero change from baseline. Discard the collected data after interruption/discontinuation of adjuvant endocrine therapy and assign the value of zero change from baseline.	N/A
1	Temporary treatment interruption ^a Due to COVID-19 /administrative or any other treatment unrelated reasons	Hypothetical strategy If participant complied with treatment. Data collected for a specific assessment during/after a temporary treatment interruption will be discarded for that assessment Week only.	Participants, from the same arm, who comply ^b with treatment regimen and have observed data at the time point that requires imputation. (same as the first supplementary analysis)
2	Temporary treatment interruption Due to AE	Treatment policy strategy Utilize all the collected data in the analysis.	Participants, from the same arm, within the same pattern who have available data before and during the treatment interruption. MI will be used to model change from a time point before treatment interruption to a time point

version 3.0 Page: 42 of 87

			with treatment interruption (Copy Increment from Reference imputation strategy). (same as the first supplementary analysis)
3	Permanent treatment discontinuation (Due to AE/lack of efficacy)	If participant remained untreated/on background therapy after permanent discontinuation of the randomized treatment, use the treatment policy strategy and utilize the collected data.	Missing values that occur after the ICE will be imputed using a similar MI model as used in the main analysis of the primary endpoint, i.e., ,the wash-out method (Wang et al. 2023) (same as the first supplementary analysis)
		Otherwise, if participant initiated an alternative treatment, use the composite strategy assuming treatment failure (i.e. no change from baseline). Discard data after the ICE and assign the value of zero change from baseline	N/A
4	Permanent treatment discontinuation. Due to COVID-19 /administrative or any other treatment unrelated reasons	Hypothetical strategy If participant did not discontinue the randomized treatment due to the specified reason. Any data collected after permanent treatment discontinuation will be discarded.	All other participants from the same arm (i.e., participants without a similar ICE at the time point that requires imputation). (same as the first supplementary analysis)

a) If more than one interruption for different reasons is recorded during the specified weeks (please see the definition of ICE in Section 1.1), the data handling rule and missing data imputation will be performed based on the reason in the following pre-specified order: 1) AE, 2) Due to COVID-19/ administrative or any other treatment unrelated reasons.

b) Complying with treatment regimen is defined as: 1) on treatment (i.e., no earlier discontinuation of randomized treatment); 2) has no treatment interruption in the respective week (according to the definition in Table 1–2) and 3) has not taken any prohibited meds.

c) Definition of interruption/discontinuation in intake of adjuvant endocrine therapy:

For participants using tamoxifen: reduction of at least 50% of planned daily dosage taken during week 1, weeks 3 and 4, weeks 7 and 8 or weeks 11 and 12 compared to baseline

For participants using aromatase inhibitor: reduction of at least 30% of planned daily dosage taken during week 1, weeks 3 and 4, weeks 7 and 8 or weeks 11 and 12 compared to baseline

version 3.0 Page: 43 of 87

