4.2.3. Supplementary Analyses

Two supplementary estimands are defined for this trial.

The hypothetical strategy will be used for handling temporary treatment interruption and permanent treatment discontinuation due to COVID-19, administrative and any other treatment unrelated reasons in both supplementary estimands. Intake of prohibited medications, discontinuation in intake of adjuvant endocrine therapy and permanent treatment discontinuation with initiation of alternative VMS treatment will be handled by the hypothetical strategy in the first supplementary estimand and by the composite strategy in the second supplementary estimand.

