6.4.2. Permanent discontinuation of randomized treatment

The reasons for permanent discontinuation of randomized treatment will be collected on the corresponding eCRF page, among others with AE or lack of efficacy as possible options. A permanent discontinuation of randomized treatment will be considered to be due to "other treatment unrelated reasons" if AE or lack of efficacy was not selected as reason and any of the following was selected:

Non-compliance with study device

version 3.0 Page: 70 of 87

- Site terminated by sponsor
- Technical problems
- Pregnancy
- Subject decision
- Subject decision: unwillingness to comply with study procedures
- Lost to follow-up
- Other
- COVID-19 pandemic related: subject specific
- COVID-19 pandemic related: other
- Non-compliance with study drug
- Randomized by mistake

The observed permanent discontinuations of randomized treatment together with corresponding reason will be presented in data listings.

Discontinuation due to AE or lack of efficacy may be handled differently depending on estimand for participants who remained untreated/background therapy and for participants who initiate alternative VMS treatment. The treatment status (i.e., remained untreated/on background therapy vs. initiate alternative VMS treatment) should be captured for all participants who discontinued from randomized drug irrespective of the reason for discontinuation.

Table 6–3: Preliminary list of alternative VMS treatment (can be updated during blind review meeting)

				I		1
DGCODEL0	DGNAME0	DGCODEL1	DGNAME1	DGCODEL2	DGNAME2	Duration of
						impact with
						respect to
						efficacy ^a
						(considered up
						to 12 weeks ^b)
		5	Hormone	2	Oestrogens	1, From 1st
			replacement			dose to 4 weeks
			therapy			after the last
						dose if the route
						is vaginal,
						intravaginal,
						cutaneous,
						nasal or
						transdermal.
						2, From 1st
						dose to 8 weeks
						after the last
						dose if the route

Page: 71 of 87 version 3.0

						is oral, sublingual or intrauterine, 3, From 1st dose to 12 weeks or longer if the route is subcutaneous or intradermal.
		5	Hormone replacement therapy	3	Progestogens	1, From 1st dose to 4 weeks after the last dose if the route is vaginal, intravaginal, cutaneous, nasal or transdermal. 2, From 1st dose to 8 weeks after the last dose if the route is oral, sublingual or intrauterine, 3, From 1st dose to 12 weeks or longer if the route is subcutaneous, intradermal or intramuscular.

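### Second supplementary estimand: the variable scores every switch to another VMS treatment after permanent discontinuation as no change, but Tables 4-6 and 4-7 do so only after AE or lack of efficacy, with no precedence rule for the rest

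*SAP*

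**What the plan says.** The text of SAP Section 4.2.3.2 says that for "permanent treatment discontinuation after which participants initiated alternative VMS treatments and interruption/discontinuation in intake of adjuvant endocrine therapy, the composite strategy will be used". The Week 4 and Week 12 variables repeat this: a participant who starts another VMS treatment after permanently stopping randomized treatment counts as unchanged from baseline. The events listed in the variable close with "initiation of alternative VSM treatment after permanent discontinuation of randomized treatment or interrupted/discontinued adjuvant endocrine therapy) or no change from baseline otherwise". Neither place limits the reason for stopping.

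The Section 4.2.3 overview is also unrestricted. It says "permanent treatment discontinuation with initiation of alternative VMS treatment will be handled by the hypothetical strategy in the first supplementary estimand"; for the second estimand it names the composite strategy instead. The sentence before it assigns permanent discontinuation for COVID-19, administrative and other treatment-unrelated reasons to the hypothetical strategy in both estimands.

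Table 4-6 places the composite row for starters of alternative treatment under the reason "AEs (treatment related/unrelated) or Lack of efficacy". The row for other reasons reads "Hypothetical If participant did not discontinue the randomized treatment" and is not split by alternative treatment. Table 4-7 follows the same layout. Pattern 3 (AE or lack of efficacy) gives switchers zero change. Pattern 4 (all other reasons) says: "If participant did not discontinue the randomized treatment due to the specified reason. Any data collected after permanent treatment discontinuation will be discarded".

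Section 6.4.2 counts subject decision, non-compliance with study drug, loss to follow-up and 'other' as treatment-unrelated whenever AE or lack of efficacy was not selected. It adds that treatment status after stopping "should be captured for all participants who discontinued from randomized drug irrespective of the reason for discontinuation".

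**The concern.** A woman who stops for a reason other than AE or lack of efficacy and then starts another VMS treatment meets two rules. The variable gives her zero change. Pattern 4 gives her an imputed value under the scenario that she had stayed on randomized treatment. Section 4.2.3 assigns her to both strategies in consecutive sentences.

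An estimand should give one value per participant per time point. Here two programmers could follow the same SAP and obtain different data sets, and one of those would not estimate the stated variable. Section 4.3.1.4 carries both supplementary estimands over to PROMIS SD SF 8b and MENQOL, so the ambiguity reaches the key secondary endpoints as well.

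**Working it through.** No figure in the plan depends on this point, so there is none to reproduce. The check compares the rules and then illustrates the size.

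**Rules side by side, for a switch after permanent discontinuation**

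| Source | AE or lack of efficacy | Any other reason |
|---|---|---|
| 4.2.3.2 text and variable | zero change | zero change |
| 4.2.3 overview | composite | composite and hypothetical, unranked |
| Table 4-6 | composite | hypothetical |
| Table 4-7 | pattern 3, zero change | pattern 4, discard and impute |

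**Does the prohibited-medication row close the gap?** That row is composite for any reason. The drugs on the preliminary alternative-treatment lists (Tables 6-3 and 6-4: oestrogens, progestogens, SSRIs, Oxybutin) all reappear in Tables 6-5 and 6-6. Table 4-6 limits the row to the period of confounding, whereas the alternative-treatment row runs from the event onward.

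A constructed example: a woman stops by her own decision on Day 20 and takes a listed SSRI from Day 22 to Day 40. Table 6-5 counts impact until 4 weeks after the last dose, so to Day 40 + 28 = 68.

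- Week 4 (Days 22-28): the prohibited-medication row gives zero change and pattern 4 gives an imputed value. Both apply and neither is ranked.
- Week 12 (Days 78-84): the impact window has closed, so only pattern 4 applies, while the variable still says zero change.

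The one ordering rule for concurrent events, note a to Table 4-7, covers temporary interruptions with different reasons. Section 6.2 orders imputation through patterns 1 to 4 but does not place the zero-change assignment in that order.

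**Size.** Let fE and fP be the shares of the elinzanetant and placebo arms that switch in this way and are left in pattern 4. Let cE and cP be the arm mean changes, and assume pattern 4 returns the arm mean on average.

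- Tables: D = cE - cP
- Variable: D = (1 - fE) × cE - (1 - fP) × cP
- Shift = -fE × cE + fP × cP

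Assumptions, not in the documents: cP from -1.5 to -3.0 HF/day and a true difference of -1.5, hence cE from -3.0 to -4.5.

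| Share affected | Shift (HF/day) | Difference under the variable |
|---|---|---|
| 1% in each arm | 0.01 × 1.5 = 0.015 | -1.485 |
| 3% in each arm | 0.03 × 1.5 = 0.045 | -1.455 |
| 5% in each arm | 0.05 × 1.5 = 0.075 | -1.425 |
| 5% elinzanetant only | 0.05 × 3.0 to 4.5 = 0.150 to 0.225 | -1.350 to -1.275 |
| 5% placebo only | -0.05 × 1.5 to 3.0 = -0.075 to -0.150 | -1.575 to -1.650 |

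For scale, 3% of 270 is about 8 women, which is 30% of the 10% drop-out that SAP Section 5 assumes for the first 3 months.

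**The case against.** The strongest reply is that the prohibited-medication row already does the work. In Table 6-5 the condition for hormones and SSRIs is a start, dose change or stop in the first 12 weeks of the study period, not while on study drug. Oxybutin carries no condition, and Section 4.1.2 flags events through Day 84. On that reading most switchers reach the composite row whatever their reason for stopping. A value already set to zero is also naturally read as not open to imputation. This largely stands, and it is why the affected group is probably small. The protocol's ban ending one week after the last dose (Table 10-4) and the post-treatment medication class in SAP Section 6.5.5 do not clearly override the SAP's own study-period condition. What remains is the time limit on the row, the missing precedence rule, and lists that are still preliminary.

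A second reply is that the tables show the intent. Section 6.4.2 links the split by alternative treatment to AE or lack of efficacy, and protocol Table 3-2 and SAP Tables 1-2 and 4-4 use the same nesting. Narrowing the variable would then reconcile the documents equally well. That is fair as a matter of consistency. Against it, the 4.2.3.2 text, both variables and a sentence in 4.2.3 are all unrestricted, and treatment status is to be captured for every discontinuation.

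A reader might infer that these women are scored as on-treatment responders and that the result is biased towards elinzanetant. The documents do not support this. Section 6.2 conditions pattern 4 on the woman's own baseline and pre-discontinuation values and estimates the model from a mixture that includes participants with other intercurrent events. The direction depends on which arm has more of these switchers. A shift in one arm's mean is also not the shift in the treatment difference.

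**Conclusion.** The inconsistency is real and confined. The stated variable and Tables 4-6 and 4-7 disagree for switchers who stopped for reasons other than AE or lack of efficacy. The prohibited-medication row narrows the gap without closing it.

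On the assumptions above, the treatment difference moves by about 0.015 HF/day at 1% per arm and 0.045 at 3% per arm. It moves more, and in either direction, if the switchers are concentrated in one arm. The documents give no counts, so these are illustrations, and they apply only to women whom the prohibited-medication row does not already set to zero.

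It would be wrong to read this as a threat to the primary result. The main estimand uses treatment policy for every intercurrent event, and the confirmatory sequence in SAP Section 2 does not include the supplementary analyses.

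**What to change.** Make the tables match the stated variable:

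1. In Tables 4-6 and 4-7, move the zero-change row for starters of alternative VMS treatment out from under AE or lack of efficacy, and apply it to permanent discontinuation for any reason.
2. State that composite assignment takes precedence over pattern 4, and correct the overlapping sentences in Section 4.2.3 accordingly.
3. Apply it week by week from the start of the alternative treatment, extending the Section 4.1.2 flagging rule to that start date. Weeks before the start stay in pattern 4. Do not classify by status at Day 84: a woman who stops on Day 15 and switches on Day 70 would then have her Week 4 value decided by a later event.

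The cost is table wording and one precedence rule in the SAP. No new data are needed, since treatment status is already to be captured for all discontinuations. A count of these switchers by arm in the report would show whether the choice mattered.

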4.3. Secondary Endpoints Analysis

4.3.1. Key Secondary Endpoints

The key secondary efficacy endpoints in this study are:

- Mean change in PROMIS SD SF 8b total T-score from baseline to Week 12
- Mean change in MENQOL total score from baseline to Week 12

4.3.1.1. Definition of Endpoints

4.3.1.1.1. Patient-reported Outcomes Measurement Information System Sleep Disturbance Short Form 8b (PROMIS SD SF 8b) related endpoints

Mean change in PROMIS SD SF 8b total T-score from baseline to Week 12

Participants responses to the 8 single items of the instrument are scored on a 5 point scale from not at all, never or very poor to very much, always or very good (four of the items are scored reversely) and aggregated to derive total raw scores ranging from 8-40. These total raw scores are then converted into total T-scores using a look-up table for comparison with population norms. Higher scores indicate greater level of sleep disturbances. See further details in Section 6.1.2.

4.3.1.1.2. Menopause Specific Quality of Life Scale (MENQOL) related endpoints

• Mean change in MENQOL total score from baseline to Week 12

Participants responses to the 29 items will be scored individually on a scale indicating whether the participant experienced the symptom (yes/no). If they select yes, they rate how bothered they were by the symptom using a 6-point verbal descriptor scale. The items assess four domains of symptoms and functioning: vasomotor symptoms, psychosocial functioning, physical functioning, and sexual functioning. Domain scores are calculated as mean of single item converted scores. The MENQOL total score is the mean of the domain mean scores. Higher scores indicate greater bother. See details in Section 6.1.3.

4.3.1.2. Main Analytical Approach

The same clinical questions are posed in respect of each primary and key secondary endpoint, and hence the data handling rules selected in respect of the ICEs are the same (detailed in Section 4.2.1). The key secondary endpoints will be analyzed using a mixed model with repeated measures (MMRM) model analogous to the main analysis of primary endpoints (see Section 4.2.1). For PROMIS SD SF 8b T-scores are used. For MENQOL week 1 data will not be collected, the analysis will be adjusted accordingly.

PROMIS SD SF 8b total scores (converted as T-scores), total raw scores and MENQOL total scores will be summarized descriptively by treatment group and week using the number of non-missing observations, arithmetic mean and standard deviation, median, minimum and maximum. The absolute values at various weeks and the corresponding change from baseline per week will be summarized accordingly. The change from baseline over time will be shown using line plots for means together with 95% CIs by treatment group.

version 3.0 Page: 44 of 87

Graphical summaries with the absolute change from baseline on the x-axis and proportion of participants achieving this reduction on the y-axis, by treatment group, for week 4 and 12 will be presented for the MENQOL total score and for the PROMIS SD SF 8b total T-score.

PROMIS SD SF 8b raw scores for each item will be summarized by a frequency table with the number of observations and percentage by treatment group and week. Bar charts will also be created by treatment group and week.

4.3.1.3. Sensitivity Analyses

The sensitivity analysis similar to described in Section 4.2.2 will be performed for key secondary endpoints.

For tipping point analysis, the adjustments will be applied with the following delta values:

- PROMIS SD SF 8b total T-score, delta values of 3, 6, 9, etc.
- MENQOL total score, delta values of 0.5, 1, 1.5, etc.

